### 9.3. Populations for Analyses

For the purposes of analysis, the following populations are defined:

Population	Description
Modified Intent-To-Treat (MITT) Population	The MITT Population includes all participants who received at least 1 dose of study intervention and have at least 1 post-baseline spot urinary oxalate to creatinine ratio. The MITT Population is for efficacy analysis.
Evaluable Population	The evaluable population includes all participants in the MITT Population who received 6 full doses of study intervention and completed through the Day 180 Study Visit.
Safety Population	All participants who received at least 1 dose of study intervention
Pharmacokinetic Population	The PK Population includes all participants who received at least 1 dose of study intervention (without major dosing violations) and have at least 1 evaluable postdose PK assessment

### 9.4. Statistical Analyses

The SAP will be finalized prior to database lock and it will include a more technical and detailed description of the statistical analyses described in this section, including the procedures for accounting for missing, unused, and spurious data.

This section is a summary of the planned statistical analyses of the most important endpoints including primary and secondary endpoints.

Sensitivity analyses may be conducted and will be described in further detail in the SAP.

#### 9.4.1. General Considerations

All statistical analyses will be descriptive in nature. No tests of statistical inference are planned.

### 9.4.2. Primary Endpoint

The primary endpoint in this study is change from Baseline to Month 6 in spot urinary oxalate-to-creatinine ratio by PH1, PH2, or PH3 participant subgroups. The percent and absolute change in average spot urinary oxalate-to-creatinine ratio from Baseline to Day 180 will be summarized by PH1, PH2, or PH3 participant subgroups.

### 9.4.3. Secondary Endpoints

#### 9.4.3.1. Efficacy Endpoints

Secondary efficacy endpoints are listed below. Additional details will be provided in the SAP.

Endpoint	Statistical Analysis
Percentage of participants with spot urinary oxalate-to-creatinine ratio $\leq$ the ULN or $\leq 1.5 \times$ ULN at any time point through Month 6	The percentage of participants with spot urinary oxalate-to-creatinine ratio $\leq$ the ULN or $\leq 1.5 \times$ ULN at any time point through Month 6 will be summarized by PH1, PH2, or PH3 participant subgroups.
Change from Baseline in eGFR at Month 6	The percent change from baseline in eGFR at Month 6 (only in participants $\geq 12$ Months of age at Screening) will be summarized by PH1, PH2, or PH3 participant subgroups.

#### 9.4.3.2. Safety Endpoints

All safety analyses will be performed on the Safety Population. The incidence and nature of TEAEs and SAEs, along with change from Baseline in 12-lead ECG, physical examination findings, vital sign assessments, and clinical laboratory tests will be summarized.

Adverse events will be defined as treatment emergent if they have an onset or worsen in severity after a participant receives the study intervention. Treatment-emergent AEs will be summarized by SOC and preferred term according to the MedDRA. Treatment-emergent AEs will be further summarized by severity and relationship to study intervention. Adverse events leading to discontinuation, SAEs, and deaths will be summarized/listed.

Descriptive statistics will be provided for absolute values and changes from baseline in physical examination findings, vital sign measurements, ECGs, and clinical laboratory results at each timepoint.

#### 9.4.3.3. Pharmacokinetic Endpoints

Pharmacokinetic analyses will be described in the SAP finalized before database lock. The population PK analysis will be presented separately from the main CSR.

#### 9.4.4. Tertiary/Exploratory Endpoint(s)

Exploratory efficacy endpoints are listed below. Additional details will be provided in the SAP.

Endpoint	Statistical Analysis
Percent and absolute change in plasma oxalate over time	The percent and absolute change in plasma oxalate will be summarized by PH1, PH2, or PH3 participant subgroups.
Change from Baseline in annualized stone event rate	The change from Baseline in annualized stone event rate will be summarized by PH1, PH2, or PH3 participant subgroups.
Change from Baseline in the Pediatric Quality of Life Inventory (PedsQL™)	The change from Baseline in the PedsQL™ will be summarized by PH1, PH2, or PH3 participant subgroups.
Change from Baseline in the Work Productivity and Activity Impairment Questionnaire: Primary Hyperoxaluria V2.0, Clinical Practice Version (WPAI:PH, V2.0, CPV) – Caregiver	The change from Baseline in the WPAI:PH, V2.0, CPV – Caregiver will be summarized by PH1, PH2, or PH3 participant subgroups.

#### 9.5. Interim Analyses

No formal interim analyses are planned, but the Sponsor reserves the right to conduct interim analyses if needed to support regulatory activities. Safety and efficacy data will be provided to the SRC on an as-needed basis.

#### 9.6. Safety Review Committee (SRC)

The SRC will review safety and efficacy data on a periodic basis as described in the SRC charter. In addition, the SRC will closely monitor any changes in the PK (as appropriate), PD, or clinical efficacy, as well as any emerging events, such as anaphylaxis or hypersensitivity reactions that may suggest the development of ADAs.

The SRC will be comprised of an independent SRC chair (pediatric nephrologist), the Principal Investigator from each study site with a participant currently in the study (either having been dosed, or about to be dosed), or their designee, the Sponsor Medical Monitor, an independent ethicist, and the CRO Medical Monitor. Further operational details, including the timing of SRC meetings, will be pre-specified in the SRC charter.

On 13-Sept-2022, the SRC reviewed safety data from four 2- to 5-year-old participants with at least 60 days of exposure in this study. No related severe AEs or related SAEs were reported in these participants. Following the safety review, the SRC affirmed that the overall risk-benefit balance remained positive and approved the enrollment of participants younger than 2 years of age.

## **10. SUPPORTING DOCUMENTATION AND OPERATIONAL CONSIDERATIONS**

### **10.1. Appendix 1: Regulatory, Ethical, and Study Oversight Considerations**

#### **10.1.1. Regulatory and Ethical Considerations**

This study will be conducted in accordance with the protocol and with the following:

- Consensus ethical principles derived from international guidelines including the Declaration of Helsinki and CIOMS International Ethical Guidelines ([CIOMS VI, 2005](#))
- Applicable ICH GCP Guidelines
- Applicable laws and regulations, including privacy laws

The protocol, protocol amendments, ICF, Investigator Brochure, and other relevant documents (e.g., advertisements) must be submitted to an IRB/IEC by the Investigator and reviewed and approved by the IRB/IEC before the study is initiated.

Any amendments to the protocol will require IRB/IEC approval before implementation of changes made to the study design, except for changes necessary to eliminate an immediate hazard to study participants. Any substantial modifications to the protocol will require competent authority approval before implementation, except for changes necessary to eliminate an immediate hazard to study participants.

The Investigator will be responsible for the following:

- Providing written summaries of the status of the study to the IRB/IEC annually or more frequently in accordance with the requirements, policies, and procedures established by the IRB/IEC
- Notifying the IRB/IEC of SAEs or other significant safety findings as required by IRB/IEC procedures
- Providing oversight of the conduct of the study at the site and adherence to requirements of 21 CFR, ICH guidelines, the IRB/IEC, European regulation 536/2014 for clinical studies (if applicable), and all other applicable local regulations

#### **10.1.2. Financial Disclosure**

Investigators and sub-investigators will provide the Sponsor with sufficient, accurate financial information as requested to allow the Sponsor to submit complete and accurate financial certification or disclosure statements to the appropriate regulatory authorities. Investigators are responsible for providing information on financial interests during the course of the study and for 1 year after completion of the study.

### **10.1.3. Informed Consent Process**

Each interested prospective participant (or legally authorized representative) will receive an informed consent document that contains study information and be given ample time to read the information and consider participation. The Investigator or his/her representative will explain the nature of the study and its risks and potential benefits to the prospective participant or his/her legally authorized representative and answer all questions regarding the study. If the participant's treating physician is also the Investigator, he/she may not administer and witness the provision of informed consent. Administration of consent must be performed by another physician from the study team, to keep the roles of physician and researcher separated.

Prospective participants must be informed that the study involves research, their participation is voluntary, and that the choice not to participate or to discontinue the study at any time will involve no penalty or loss of benefits to which the individual is otherwise entitled. Consenting participants, or their legally authorized representative (parent or legal guardian for participants younger than 18 years or the local age of majority), will be required to sign a statement of informed consent that meets the requirements of 21 CFR 50, local regulations, ICH guidelines, Health Insurance Portability and Accountability Act (HIPAA) requirements, where applicable, and the IRB/IEC or study center. For children younger than 12 years of age, assent will be based on local regulations.

The medical record must include a statement that written informed consent was obtained before the participant was enrolled in the study and the date the written consent was obtained. The authorized person obtaining the informed consent must also sign the ICF.

Participants must be re-consented to the most current version of the ICF(s) during their participation in the study. As children and adolescents age, they must be re-consented to the appropriate ICF based on current age. Participants must be informed of any new information that arises during the course of the study which might be relevant to their willingness to continue in the study.

A copy of the ICF(s) must be provided to the participant or the participant's legally authorized representative.

### **10.1.4. Data Protection**

Participants will be assigned a unique identifier by the Sponsor. Any participant records or datasets that are transferred to the Sponsor will contain the identifier only; participant names or any information which would make the participant identifiable will not be transferred.

The participant (or legally authorized representative) must be informed that his/her personal study-related data will be used by the Sponsor in accordance with local data protection law, including the General Data Protection Regulation for all clinical studies conducted in the European Union. The level of disclosure must also be explained to the participant (or legally authorized representative) who will be required to give consent for their data to be used as described in the informed consent.

The participant (or legally authorized representative) must be informed that his/her medical records may be examined by Clinical Quality Assurance auditors or other authorized personnel appointed by the Sponsor, by appropriate IRB/IEC members, and by inspectors from regulatory authorities.

#### **10.1.5. Dissemination of Clinical Study Data**

After completion and publication of the study, and de-identification, all individual data collected during the trial will be shared with investigators, whose proposed use of the data will have been approved by an independent review committee immediately following the publication of the entire study results.

Study results will be posted to the European Clinical Trials database (EudraCT) not later than 6 months after the database is locked. Study results will be posted at [www.clinicaltrials.gov](http://www.clinicaltrials.gov) not later than 12 months after the database is locked.

#### **10.1.6. Data Quality Assurance**

All participant data relating to the study will be recorded on printed or eCRF unless transmitted to the Sponsor or designee electronically (e.g., laboratory data). The Investigator is responsible for verifying that data entries are accurate and correct by physically or electronically signing the eCRF.

The Investigator must maintain accurate documentation (source data) that supports the information entered in the eCRF.

The Investigator must permit study-related monitoring, audits, IRB/IEC review, and regulatory agency inspections and provide direct access to source data documents.

Monitoring details describing strategy (e.g., risk-based initiatives in operations and quality such as Risk Management and Mitigation Strategies and Analytical Risk-Based Monitoring), methods, responsibilities and requirements, including handling of noncompliance issues and monitoring techniques (central, remote, or on-site monitoring) are provided in the Monitoring Plan.

The Sponsor or designee is responsible for the data management of this study including quality checking of the data.

The Sponsor assumes accountability for actions delegated to other individuals (e.g., CROs).

Study monitors will perform ongoing source data verification to confirm that data entered into the eCRF by authorized site personnel are accurate, complete, and verifiable from source documents; that the safety and rights of participants are being protected; and that the study is being conducted in accordance with the currently approved protocol and any other study agreements, ICH GCP, and all applicable regulatory requirements.

Records and documents, including signed ICFs, pertaining to the conduct of this study must be retained by the Investigator for 2 years after study completion unless local regulations or institutional policies require a longer retention period. No records may be destroyed during the retention period without the written approval of the Sponsor. No records may be transferred to another location or party without written notification to the Sponsor.

#### **10.1.7. Source Documents**

Source documents provide evidence for the existence of the participant and substantiate the integrity of the data collected. Source documents are filed at the Investigator's site.

Data entered in the eCRF that are transcribed from source documents must be consistent with the source documents or the discrepancies must be explained. The Investigator may need to request

previous medical records or transfer records, depending on the study. Also, current medical records must be available.

#### **10.1.8. Study and Site Start and Closure**

The Sponsor designee reserves the right to close the study site or terminate the study at any time for any reason at the sole discretion of the Sponsor. Study sites will be closed upon study completion. A study site is considered closed when all required documents and study supplies have been collected and a study-site closure visit has been performed.

The Investigator may initiate study-site closure at any time, provided there is reasonable cause and sufficient notice is given in advance of the intended termination.

Reasons for the early closure of a study site by the Sponsor or Investigator may include but are not limited to:

1. Investigator noncompliance with the protocol, GCP, or regulatory requirements
2. Unsatisfactory enrollment with respect to quantity or quality
3. Incomplete data collection; inaccurate or knowingly false data submission
4. The Principal Investigator is no longer capable of performing the tasks of the principal investigator, and no replacement can be found.
5. The SRC determines that termination of the study is in the best interest of the research participants
6. The Sponsor, Investigator or IRB/IEC determines that continuation of the study will not serve any scientific purpose
7. Circumstances beyond the control of the Sponsor or Investigator make it unreasonable to require the study's continuation
8. A request to discontinue the study by a regulatory or health authority

If the study is prematurely terminated or suspended, the Sponsor shall promptly inform the Investigators, the IECs/IRBs, the regulatory authorities, and any CRO(s) used in the study of the reason for termination or suspension, as specified by the applicable regulatory requirements. The Investigator shall promptly inform the participant and should assure appropriate participant therapy and/or follow-up.

#### **10.1.9. Publication Policy**

The results of this study may be published or presented at scientific meetings. If this is foreseen, the Investigator agrees to submit all manuscripts or abstracts to the Sponsor before submission. This allows the Sponsor to protect proprietary information and to provide comments.

The Sponsor will comply with the requirements for publication of study results. In accordance with standard editorial and ethical practice, the Sponsor will generally support publication of multicenter studies only in their entirety and not as individual site data. In this case, a coordinating Investigator will be designated by mutual agreement.

Authorship will be determined by mutual agreement and in line with International Committee of Medical Journal Editors authorship requirements.

10.2.      **Appendix 2: Clinical Laboratory Tests**

Table 3 summarizes the parameters that will be determined spot urine collections. Additional laboratory results may be reported on these samples. These additional tests would not require additional collection of urine.

**Table 3:      Parameters Determined from Urine**

Laboratory Assessment	Parameters
Spot urine	urinary oxalate urinary creatinine urinary oxalate-to-creatinine ratio

The tests detailed in Table 4 will be performed by the central laboratory.

Protocol-specific requirements for inclusion or exclusion of participants are detailed in Section 5 of the protocol.

Additional tests may be performed at any time during the study as determined necessary by the Investigator or required by local regulations.

**Table 4: Protocol-Required Safety Laboratory Assessments**

Laboratory Assessments	Parameters	
Hematology	red blood cell count hemoglobin hematocrit mean corpuscular volume (MCV) mean corpuscular hemoglobin (MCH) mean corpuscular hemoglobin concentration (MCHC) reticulocytes platelet count mean platelet volume (MPV)	White blood cell count: Lymphocytes, abs and % Monocytes, abs and % Eosinophils, abs and % Neutrophils, abs and % Basophils, abs and %
Clinical Chemistry	alanine transaminase (ALT) aspartate transaminase (AST) glutamate dehydrogenase (GLDH) gamma-glutamyl transferase (GGT) alkaline phosphatase (ALP) bilirubin (total and direct) lactate dehydrogenase (LDH) total protein albumin	creatine kinase (CK) sodium chloride potassium creatinine blood urea nitrogen (BUN)  cystatin C (for calculation of eGFR)
Routine Urinalysis	specific gravity pH, glucose, protein, blood, ketones, bilirubin, urobilinogen, nitrite, leukocyte esterase by dipstick microscopic examination (if blood or protein is abnormal)	
Pregnancy testing	Serum or urine human chorionic gonadotropin (hCG) pregnancy test (WOCBP)	
Coagulation Parameters	International normalized ratio (INR) Prothrombin time (PT)	
Antibodies	Antidrug antibodies (samples will be tested when an assay is available)	
Other Tests	Plasma oxalate	

Investigators must document their review of each laboratory safety report.

### 10.3. Appendix 3: Volume of Blood

The maximum blood volume to be collected from pediatric participants over the course of the study will be based on weight and will not exceed those specified in [Table 5](#). Consult the Laboratory Manual for the blood draw priority list based on participant weight.

**Table 5: Maximum Allowable Research-related Blood Sample Volumes**

Body Weight (kg)	Circulating Total Blood Volume (mL)	Max. Allowable Sample Volume over 4 Weeks (mL) – 3% of Total Blood Volume	Max. Allowable Sample Volume at Single Time (mL) – 1% of Total Blood Volume
0.5 – 1.5	50 – 150	1.5 – 4.5	0.5 – 1.5
2.5 – 5	250 – 500	7.5 – 15	2.5 – 5
5 – 12	480 – 960	14.4 – 28.8	4.8 – 9.6
12 – 20	960 – 1600	28.8 – 48	9.6 – 16
20 – 30	1600 – 2400	48 – 72	16 – 24
30 – 70	2400 – 5600	48 – 168	24 – 56

Note: Total blood volume is approximately 80 to 90 mL/kg body weight, in neonates approximately 100 mL/kg body weight. Of note: when routine health care requires significant blood sampling, these maximums may even be excessive.

Source: European Commission's *Ethical Considerations for Clinical Trials on Medicinal Products Conducted with Minors* ([18 September 2017](#))

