#### **Key exclusion criteria include**

- Renal or hepatic transplantation (prior or planned within the study period)
- Plasma oxalate (Pox)  $> 30 \text{ } \mu\text{mol/L}$  at Screening
- Documented evidence of clinical manifestations of severe systemic oxalosis (including preexisting retinal, heart, or skin calcifications, or history of severe bone pain, pathological fractures, or bone deformations)

**Number of Participants:** Approximately 25 participants will be enrolled such that approximately 20 participants (approximately 7 aged 6 to 11 years; approximately 10 aged 1 to

[figure not shown]
5 years; and approximately 3 aged < 1 year) complete the study, with an overall goal of approximately 15 PH1.

**Intervention Groups and Duration of Participation:** This study has a single intervention group in which all participants will receive monthly SC doses of nedosiran over a 6-month period. Prospective participants will be screened over an up-to-35-day period, with an extra 14 days allowed for participants who are required to repeat initially unanalyzable screening laboratory assessment samples. The total time on study for each participant is approximately 7 months.

**Study Duration:** Approximately 24 months from the first participant, first visit, to the last participant, last visit.

**Safety Review Committee:** This study will utilize an SRC to review safety and efficacy data on a periodic basis.

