#### **2.3.4. Risk Management**

Measures to minimize the risks to participants have been incorporated into the following study design elements:

- An SRC will review all safety and efficacy data after the first 2 participants aged 2 to 5 years old have completed Day 60 and every 3 months thereafter. Ad hoc meetings may also occur if needed as specified in the SRC charter.
- Clinical Laboratory Monitoring: At time of study entry, study participants are required to have safety laboratory values within acceptable ranges. Serial measurements of safety laboratory parameters (CBC, platelet count, creatinine, cytokines, complement, LFTs) and coagulation parameters are planned, with regular medical review by the medical monitor, as outlined in the medical management plan.
- Monitoring of signs and symptoms of muscle pain and/or weakness, along with measurement of plasma creatine kinase.
- The maximum blood volume to be collected from pediatric participants over the course of the study will be based on weight and will not exceed those specified in [Table 5](#). Consult the Laboratory Manual for the blood draw priority list based on participant weight.
- If met with blood draw difficulty, the Investigator team will make not more than 3 attempts at venipuncture in the same day.

With regard to pediatric participants, the International Conference on Harmonisation (ICH) Harmonised Tripartite Guideline: *Clinical Investigation of Medicinal Products in the Pediatric Population* ([E11, 20 July 2000](#)) and the European Commission *Ethical Considerations for Clinical Trials on Medicinal Products Conducted with Minors* ([18 September 2017](#)) have been considered during the design of the trial, and blood volume minimized where possible. Practical considerations include the use of laboratories experienced in handling small volumes of blood for PK, PD, and laboratory safety analyses.

Wherever possible, routine clinical safety, efficacy, and PK blood samples will be collected at the same time point. Furthermore, indwelling catheters will be used where deemed appropriate by the Investigator team to minimize the potential distress of venipuncture.

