#### Age

1. Birth to 11 years of age inclusive, at the time of signing the informed consent.

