### **8.2.6. Clinical Safety Laboratory Assessments**

See [Table 4](#) for the list of clinical laboratory tests to be performed and the SoA for the timing and frequency. See [Section 10.3](#) for directives regarding prioritization of blood draws.

The Investigator must review the laboratory report, document this review, and record any clinically relevant changes occurring during the study in the AE section of the eCRF. The laboratory reports must be filed with the source documents. Clinically significant abnormal laboratory findings are those which are not associated with the underlying disease, unless judged by the Investigator to be more severe than expected for the participant's condition.

All laboratory tests with values considered clinically significantly abnormal during participation in the study should be repeated until the values return to normal or baseline or are no longer considered clinically significant by the Investigator or medical monitor.

- If such values do not return to normal/baseline within a period of time judged reasonable by the Investigator, the etiology should be identified and the Sponsor notified.
- All protocol-required laboratory assessments, as defined in [Table 4](#), must be conducted in accordance with the laboratory manual and the SoA.

- If laboratory values from non-protocol specified laboratory assessments performed at the institution's local laboratory require a change in participant management or are considered clinically significant by the Investigator (e.g., SAE or AE or dose modification), then the results must be recorded in the eCRF.

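### Table 5 gives a 30 kg child two 4-week blood limits, 72 mL and 48 mL; the column's own 3% rule gives 72 mL

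*Protocol*

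**What the plan says.** Table 5 in Protocol Section 10.3 (Appendix 3) lists, for each body-weight band, the circulating total blood volume and two sampling limits. The first limit is headed "Max. Allowable Sample Volume over 4 Weeks (mL) – 3% of Total Blood Volume" and the second "Max. Allowable Sample Volume at Single Time (mL) – 1% of Total Blood Volume". The table note adds: "Total blood volume is approximately 80 to 90 mL/kg body weight, in neonates approximately 100 mL/kg body weight".

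Two rows meet at 30 kg:

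| Row | Total volume (mL) | 4-week limit (mL) | Single-draw limit (mL) |
|---|---|---|---|
| 20–30 kg | 1600–2400 | 48–72 | 16–24 |
| 30–70 kg | 2400–5600 | 48–168 | 24–56 |

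The table is binding. Section 2.3.4 says the blood volume collected "will be based on weight and will not exceed those specified in" Table 5, and Section 10.3 repeats it: "over the course of the study will be based on weight and will not exceed those specified in" the same table. Section 8.2.6 sends sites to Section 10.3 "for directives regarding prioritization of blood draws". Sections 2.3.4 and 10.3 both point to a weight-based priority list in the Laboratory Manual.

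**The concern.** At 30 kg the two rows agree on total volume (2400 mL) and on the single-draw limit (24 mL) but give 4-week limits of 72 mL and 48 mL. Both cannot be 3% of 2400 mL.

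The 30–70 kg row can apply in this trial. Inclusion criterion 1 reads "Birth to 11 years of age inclusive, at the time of signing the informed consent", Sections 5.1 and 5.2 set no upper weight limit, and the Synopsis plans for "approximately 7 aged 6 to 11 years" among the completers. The dosing rule also allows for children in this band: at 3.5 mg/kg, the 170 mg cap takes effect only above 170 / 3.5 = 48.6 kg.

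What is at stake is conduct, not inference. A site that took 48 mL as the limit for a child at or somewhat above 30 kg could drop scheduled samples that the 3% rule allows.

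**Working it through.** **Inputs**, all from Table 5: the total blood volume at each end of the six rows, the 3% rule and the 1% rule from the column headings, and the limits as listed.

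**Formulas.** 4-week limit = 0.03 × total volume. Single-draw limit = 0.01 × total volume.

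**Check of every endpoint:**

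| Weight (kg) | Volume (mL) | 3% (mL) | Listed 4-week (mL) | 1% (mL) | Listed single draw (mL) |
|---|---|---|---|---|---|
| 0.5 | 50 | 1.5 | 1.5 | 0.5 | 0.5 |
| 1.5 | 150 | 4.5 | 4.5 | 1.5 | 1.5 |
| 2.5 | 250 | 7.5 | 7.5 | 2.5 | 2.5 |
| 5 (upper end) | 500 | 15 | 15 | 5 | 5 |
| 5 (lower end) | 480 | 14.4 | 14.4 | 4.8 | 4.8 |
| 12 (upper end) | 960 | 28.8 | 28.8 | 9.6 | 9.6 |
| 12 (lower end) | 960 | 28.8 | 28.8 | 9.6 | 9.6 |
| 20 (upper end) | 1600 | 48 | 48 | 16 | 16 |
| 20 (lower end) | 1600 | 48 | 48 | 16 | 16 |
| 30 (upper end) | 2400 | 72 | 72 | 24 | 24 |
| **30 (lower end)** | **2400** | **72** | **48** | **24** | **24** |
| 70 | 5600 | 168 | 168 | 56 | 56 |

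Eleven of 12 four-week endpoints and all 12 single-draw endpoints reproduce exactly. The only mismatch is the lower end of the 30–70 kg row.

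**Size of the mismatch.** 72 − 48 = 24 mL, and 48 / 2400 = 2.0%. The listed value equals 0.03 × 1600 = 48 mL, the limit for a 20 kg child. It is also 48 / 24 = 2 single-draw maxima, where every other endpoint allows 3.

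**Could another blood volume explain 48 mL?** No. At the note's 80 to 90 mL/kg, 30 kg gives 2400 to 2700 mL, and 3% of that is 72 to 81 mL.

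**Effect above 30 kg.** The protocol does not say how to read a limit inside a band. If a site interpolates linearly (my assumption), the slope is (168 − 48) / (70 − 30) = 3 mL per kg, so the limit is 48 + 3 × (weight − 30). At 35 kg that is 63 mL, against 0.03 × 80 × 35 = 84 mL under the 3% rule. The interpolated limit does not return to 72 mL until 38 kg, so children between 30 and 38 kg would have a lower limit than the row above gives at 30 kg.

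**The case against.** The arithmetic is not in dispute; the case on the other side concerns consequence and remedy.

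- **The error is on the safe side.** Staying within 48 mL satisfies both rows, so no child is exposed to excess sampling. This stands.
- **The limit may never bind.** With a single-draw cap of 24 mL at 30 kg, exceeding 48 mL takes more than two maximum-size draws within 4 weeks. The Schedule of Activities spaces the main blood visits about 30 days apart, its footnote b keeps screening samples at least 28 days before Day 1, and Days 60 and 120 need only chemistry blood. On the other side, Days 1 and 150 have several PK samples, and the visit windows can bring two visits within 28 days: with its 2-day window, the Day 30 visit can fall on Day 28, which is 28 − 1 = 27 days after Day 1. No draw volumes are given, so dropped samples are a possibility, not a demonstrated effect.
- **Sites can apply the 3% themselves.** The heading states the rule and the adjoining cell gives 2400 mL, so a careful site would reach 72 mL. Sites may in any case work from the Laboratory Manual, which is not available here. Both points lower the risk, but neither makes the cell correct.
- **Rows also differ at 5 kg** (15 and 14.4 mL). That is true, but each is 3% of its own listed volume (500 and 480 mL). The defect at 30 kg is the broken percentage, not merely two rows disagreeing.
- **The 48 may come from the cited European Commission document.** The documents cannot settle this. It would explain the value but not remove the conflict with the 3% heading. It is a reason to check the source before changing the cell.

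**Conclusion.** The concern holds. The lower end of the 4-week limit in the 30–70 kg row is wrong as written: 48 mL where the column's rule and the adjacent row both give 72 mL, a shortfall of 24 mL per 4 weeks at 30 kg. This rests only on Table 5 as printed and on its stated 3% rule; the behaviour above 30 kg depends in addition on the assumed linear interpolation. Severity is minor. The error is conservative and bears on blood-draw limits only, and whether it would ever cost a sample cannot be determined without the draw volumes. It is more than a slip in background text because the protocol treats the table as an operating limit.

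**What to change.** In Table 5, change the 4-week limit in the 30–70 kg row from 48–168 mL to 72–168 mL, after comparing the cell with the cited source document. Confirm that the weight-based priority list in the Laboratory Manual uses the corrected value. If the sponsor does intend 48 mL at 30 kg, state it as an exception to the 3% rule and align the upper end of the 20–30 kg row, so that one weight has one limit.

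The cost is a one-cell correction by clarification letter or at the next amendment, plus the Laboratory Manual check. The SAP needs no change.
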